### **3.7. Analysis Visit Windows**

#### **3.7.1. Definitions**

The First Dosing Date is defined as the date when subjects take the first dose of study drug, as recorded in the Study Drug Administration eCRF.

The Last Dosing Date is defined as the date when subjects take the last dose of study drug as recorded in the Study Drug Administration eCRF.

Study Day will be calculated from the first dosing date of study drug and derived as follows:

- For days on or after first dosing date: Assessment Date – First Dosing Date + 1
- For days prior to the first dosing date: Assessment Date – First Dosing Date

Therefore, Study Day 1 is the day of the first dose of study drug administration.

Baseline is defined as the last available observation prior to or on the first dosing date, unless specified otherwise.

#### **3.7.2. Analysis Visit Windows**

Subject visits might not occur on protocol-specified days. Therefore, for the purpose of analysis, observations will be assigned to analysis windows.

CCI

CCI

The analysis windows for weight, vital signs, ECG, safety laboratory parameters (hematology, chemistry, fasting lipid profile, serum immunoglobulin), and key inflammatory biomarkers (including hs-CRP, fecal calprotectin, and fecal lactoferrin) are provided in [Table 3-4](#).

CCI

**Table 3-4. Analysis Visit Windows for: Weight, Vital Signs, ECG, Hematology, Chemistry, Fasting Lipid Profile, Serum Immunoglobulin, CCI**

Nominal Visit	Analysis Visit	Nominal Day (Study Day)	Lower Limit (Study Day)	Upper Limit (Study Day)
Screening/Day 1	Baseline	1	(none)	1
Week 2	Week 2	15	2	22
Week 4	Week 4	29	23	36
Week 6	Week 6	43	37	57
Week 10	Week 10	71	58	85
Week 14	Week 14	99	86	113
Week 18	Week 18	127	114	141
Week 24	Week 24	169	142	≥ 169

Note: ECG is collected postbaseline at Week 10 and the corresponding analysis windows will be applied; fasting lipid profile, fecal lactoferrin, and fecal calprotectin are collected postbaseline at Weeks 10 and 24 and the corresponding analysis windows will be applied; serum immunoglobulin is collected postbaseline at Weeks 4, 10, and 24 and the corresponding analysis windows will be applied.

An unscheduled visit prior to the first dosing of study drug may be included in the calculation of the baseline value, if applicable.

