- INR > 1.5
- or accompanied by symptoms consistent with hepatic injury

For any subject with an initial AST or ALT elevation > 3 x ULN, at the time of the second confirmatory draw, an INR, prothrombin time (PT), and partial thromboplastin time (PTT) must also be drawn.

Two sequential AST or ALT > 5 x ULN

Two sequential values for estimated creatinine clearance (CL_{cr}) < 35 mL/min based on the Cockcroft-Gault (CC&G) formula

$$\text{Male: } \frac{(140 - \text{age in years}) \times (\text{wt in kg})}{72 \times (\text{serum creatinine in mg/dL})} \text{ } CL_{cr} \text{ (mL/min)}$$

$$\text{Female: } \frac{(140 - \text{age in years}) \times (\text{wt in kg}) \times 0.85}{72 \times (\text{serum creatinine in mg/dL})} \text{ } CL_{cr} \text{ (mL/min)}$$

Subjects are free to withdraw from the study at any time without providing reason(s) for withdrawal and without prejudice to further treatment. The reason(s) for withdrawal will be documented in the electronic case report form (eCRF).

Subjects who permanently discontinue study drug for any reason should discuss their continued care plan with their physician.

Subjects who permanently discontinue study drug for pregnancy should not continue in the study; if there are any questions regarding permanent discontinuation, these should be discussed with the Sponsor.

Subjects withdrawing from the study should complete Early Termination (ET), followed by PTx assessments 30 days after the last dose of study drug (Refer to Section 6.13 for Post Treatment assessments).

Reasonable efforts will be made to contact subjects who are lost to follow-up. All contacts and contact attempts must be documented in the subject's file.

The Sponsor has the right to terminate the study at any time in case of safety concerns or if special circumstances concerning the study medication or the company itself occur, making further treatment of subjects impossible. In this event, the investigator(s) and relevant authorities will be informed of the reason for study termination.

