6.13. Post-Treatment Assessments

All subjects must complete the PTx assessments 30 days after the last dose of study drug. Only subjects who choose to participate in the LTE study will not complete PTx assessments associated with this protocol:

- Symptom-directed PE including perianal assessment
- Obtain body weight and vital signs (resting blood pressure, respiratory rate, pulse, and temperature)
- Review AEs and concomitant medications
- Obtain blood samples (see Study Procedures Table [[Appendix 2](#)])
- Obtain urine sample for pregnancy test (for females of childbearing potential only)

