## 7. SAFETY ANALYSES

Unless otherwise specified, summaries of safety data will be provided for the Safety Analysis Set and will include data collected up to the last dose of study drug plus 30 days.

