		1	2	3	4	5	6	7	8	9	10	PTx a	ET
Visit													
Week		0	2	4	6	10	14	18	20	24			
Study Day	-30 to -1	1	15	29	43	71	99	127	141	169			
Visit Window (±)			±3	±3	±3	±2	±3	±3	±5	±5	±3		
CCI													
CCI													
CCI													

a The Post-Treatment (PTx) visit should occur 30 days after the last dose of study drug. Only subjects who roll over into the LTE study will not complete PTx assessments.

b For subjects who terminate prior to Week 10

c A complete physical examination (PE) including; vital signs, body weight, height, and perianal assessment (including completion of the Perianal Fistula Assessment Worksheet) will be performed at screening. A symptom-directed PE and perianal assessment(including completion of the Perianal Fistula Assessment Worksheet) should be performed at all other time points.

e Subjects should begin filling out the eDiary the day of their initial screening visit and continue to fill it out throughout the remainder of the study.

f Refer to Section 6.6 of study protocol for details on the MRI procedure

g Positive cocaine test disqualifies subject; positive amphetamines, barbiturates, benzodiazepines, and opioids require medical monitor review

h All females meeting the childbearing potential criteria must have a serum pregnancy testing at screening and a urine pregnancy test must be completed every 4 weeks at a minimum. If any pregnancy test is positive, study drug must be immediately interrupted and the subject should come to the site for serum pregnancy test in clinic.

i Proof of no active or untreated latent TB at screening. Subjects who are diagnosed with latent TB at screening must initiate an adequate course of prophylaxis as per local standard of care, for a minimum of 4 weeks prior to randomization. Subject may initiate study drug dosing only after consultation with the Study Medical Monitor.

j An HIV-1/HIV-2 antibody test, a HCV antibody test, a HBV surface antigen test, a HBV surface antibody test, and a HBV core antibody test will be performed on all subjects; subjects with any positivity will be excluded unless the Hepatitis B surface antibody is the sole positive result (indicating immunization)

k TCR: T-cell receptor; BCR: B-cell receptor

o Refer to Section 6.5 of study protocol for details on the flexible sigmoidoscopy procedure

p Subjects should fast (no food or drinks, except water) for at least 8 hours prior to blood sample collection at Day 1, Week 10, and Week 24

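### SAP Table 3-4 has no post-treatment visit, so off-drug follow-up values of some early leavers are reported as later on-treatment visits

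*SAP*

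**What the plan says.** - **Windowing (SAP 3.7.1, 3.7.2).** "Study Day will be calculated from the first dosing date of study drug", and "for the purpose of analysis, observations will be assigned to analysis windows". A typical row of Table 3-4 is "Week 14 Week 14 99 86 113" (nominal day, lower limit, upper limit). The last row is "Week 24 Week 24 169 142 ≥ 169", which has no finite upper limit. There is no post-treatment row and no condition on the last dosing date.
- **Selection (SAP 3.7.3).** If a window holds several post-baseline records, the one nearest the nominal day is used; on a tie, the later one.
- **PTx visit.** Protocol 6.13: "All subjects must complete the PTx assessments 30 days after the last dose of study drug". SAP Appendix 1 repeats the timing: "The Post-Treatment (PTx) visit should occur 30 days after the last dose of study drug". Subjects who go into the LTE are exempt. Protocol 3.5.2 covers early leavers: "Subjects withdrawing from the study should complete Early Termination (ET), followed by PTx assessments 30 days after the last dose of study drug". In the schedule of assessments, the PTx column includes hematology, chemistry, CRP, serum immunoglobulin, weight and vital signs, with a visit tolerance of ±3 days.
- **Data cut-off (SAP 7).** Safety summaries "will include data collected up to the last dose of study drug plus 30 days". SAP 7.2 sets the same limit for laboratory data.
- **Use of the windows.** SAP 7.2.1 and 7.3 summarise values and changes from baseline at each post-baseline time point. SAP 7.2.1 also plots median (Q1, Q3) change for selected laboratory tests.

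**The concern.** Study day from first dose does not show whether a subject is still on drug. The 30-day cut-off keeps an on-schedule PTx sample in the safety data, and Table 3-4 gives it nowhere to go except a treated-visit row. Followed as written, the rules label a value taken about a month off drug as Week 10, 14, 18 or 24.

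The by-visit tables and plots are meant to show what happens to counts, enzymes and vital signs during treatment. If an effect reverses off drug, the misplaced values pull the summary toward baseline. The subjects involved may be the informative ones: Protocol 3.5.2 requires permanent discontinuation for confirmed low neutrophil or platelet counts, raised transaminases or low creatinine clearance. A value that has recovered off drug in such a subject could be shown as the next treated value of the same parameter.

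**Working it through.** **1. Reproduce the table's limits.** The upper limit should be the midpoint of consecutive nominal days (15, 29, 43, 71, 99, 127, 169).
- (15+29)/2 = 22; (29+43)/2 = 36; (43+71)/2 = 57; (71+99)/2 = 85; (99+127)/2 = 113. All five match Table 3-4.
- (127+169)/2 = 148, but the table has 141. The revision log in SAP 12 records the Week 18 and Week 24 windows as a deliberate change.

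**2. Subjects who stop on a scheduled visit day.** PTx day = last dose day + 30.

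| Last dose | PTx day | Window hit | Reported as | Days from nominal |
|---|---|---|---|---|
| 15 (Week 2) | 45 | 37–57 | Week 6 | 2 |
| 29 (Week 4) | 59 | 58–85 | Week 10 | 12 |
| 43 (Week 6) | 73 | 58–85 | Week 10 | 2 |
| 71 (Week 10) | 101 | 86–113 | Week 14 | 2 |
| 99 (Week 14) | 129 | 114–141 | Week 18 | 2 |
| 127 (Week 18) | 157 | 142–open | Week 24 | 12 |

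Leavers at Week 2 or Week 4 skip one visit. Immunoglobulin uses only the Week 4, 10 and 24 windows, so of these rows only Days 59, 73 and 157 affect it.

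**3. Every early last-dose day L = 1 to 168, PTx at L + 30.** Assumption: the early-termination (ET) sample is taken on the last dosing day.
- L = 1 to 141: no closed post-baseline window is longer than 28 days, so a 30-day shift always reaches a later window. No on-drug record competes, and the PTx value is used. That is 141 days.
- L = 142 to 168: both samples fall in the Week 24 window. The PTx sample is L − 139 days from Day 169 and the ET sample 169 − L days. PTx is selected when L − 139 ≤ 169 − L, that is L ≤ 154. That gives 13 days (142 to 154) to PTx and 14 days (155 to 168) to ET.
- Total: 141 + 13 = 154 of 168. With PTx at +27, +28 or +29 the totals are 152, 155 and 154.
- At +30 the window hit is that of the next nominal visit for 81 last-dose days, one visit further for 78 and two further for 9 (81 + 78 + 9 = 168).

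These are counts of possible days, not of subjects.

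**4. Completers.** A Week 24 sample within ±5 days (Days 164 to 174) is at most 5 days from nominal. With the last dose on that visit day, PTx is at Days 194 to 204, which is 25 to 35 days away, so the Week 24 sample is used. If it is missing, a PTx sample at, say, 169 + 30 = Day 199 still falls in the open window and becomes Week 24.

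**5. Size.** With *k* affected subjects in an arm of 30, all of whom have a value at that visit, the off-drug share is *k*/30: 1/30 = 3%, 5/30 = 17%. If the effect reverses fully off drug, a mean shift shrinks by the same fraction. This does not carry over to the median plots. The range 1 to 5 is an assumption.

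**The case against.** The strongest case on the other side is that the scope is narrow and the consequence small. Much of it stands.

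- **Not every early leaver is affected.** A reader might infer that each one is. LTE entrants have no PTx visit, and subjects who exit for Week 10 non-response or later worsening are the ones offered the LTE, if eligible. PTx samples at +31 to +33 days are inside the visit tolerance but beyond the cut-off, so they drop out of the safety summaries.
- **Week 24 is not unbounded for safety data.** The open limit is in the table; the +30-day rule caps it. For hs-CRP, which also uses Table 3-4, no visible text supplies a cap.
- **Not always the next visit**, as steps 2 and 3 show.
- **Not every parameter.** ECG and fasting lipids are not scheduled at PTx.
- **No documented difference between arms.** It is tempting to say that the dilution differs by arm because early exit does. Neither document gives exit rates by arm, so that is conjecture.
- **Low stakes.** No formal testing is planned, and the chronological by-subject listings still show the values.

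Two further objections carry less weight. The first is that the SAP is merely silent on PTx records. But the visible rule assigns observations to windows, the cut-off retains PTx samples, and nothing visible exempts them. The second is that parts of SAP 3.7.2 are redacted. A rule there cannot be excluded, but Table 3-4 shows none.

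**Conclusion.** The point holds in a limited form. The visible rules place off-drug hematology, chemistry, weight and vital-sign values, and in some windows immunoglobulin, in on-treatment rows. This applies to subjects who stop early, do not enter the LTE and are sampled by day +30, and to completers who lack a Week 24 sample. For early leavers it happens for 154 of 168 possible last-dose days, assuming that the ET sample is taken on the last dosing day and PTx is at +30.

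Only the descriptive by-visit summaries and plots are affected. The number of subjects is unknown, so the 3% to 17% share is illustrative, and bias between arms is not established. The SAP should be corrected because a stated rule gives a mislabelled result, but the trial's main conclusions do not depend on it.

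**What to change.** In SAP 3.7.2:

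1. Map Table 3-4 records taken more than a small, stated allowance after the last dose to a separate 'Post-treatment' analysis visit. The earliest scheduled PTx sample is at +27 days, so an allowance well below that separates the two.
2. Restrict the Week 2 to Week 24 rows to on-treatment records. This also bounds Week 24, including for hs-CRP.
3. Keep the 30-day window for adverse-event and toxicity-grade tables.
4. State whether PTx samples at +31 to +33 days belong in the new row.

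The number of last-dose days for which a PTx value is reported as a treated visit falls from 154 to 0. The cost is SAP wording and one programming rule. The downside is slightly fewer values in the later visit rows.

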### **3.7.3. Selection of Data in the Event of Multiple Records in an Analysis Visit Window**

Depending on the statistical analysis method, single values may be required for each analysis window. For example, change from baseline by visit usually requires a single value, whereas a time-to-event analysis would not require 1 value per analysis window.

If multiple, valid, nonmissing, continuous measurements exist in an analysis window, records will be chosen based on the following rules if a single value is needed:

- In general, the baseline value will be the last nonmissing value on or prior to the first dosing date of study drug, unless otherwise specified. If multiple measurements occur on the same day, the last nonmissing value prior to the first dosing date of study drug will be considered as the baseline value. If these multiple measurements occur at the same time or the time is not available, the average of these measurements (for continuous data) will be considered the baseline value.
- For postbaseline visits:
  - The record closest to the nominal day for that visit will be selected.
  - If there are 2 records that are equidistant from the nominal day, the later record will be selected.
  - If there is more than 1 record on the selected day, the average will be taken, unless otherwise specified.

If multiple, valid, nonmissing, categorical measurements exist in an analysis window, records will be chosen based on the following rules if a single value is needed:

- For baseline, the last available record on or prior to the date of the first dose of study drug will be selected. If there are multiple records with the same time or no time recorded on the same day, the value with the lowest severity will be selected (eg, normal will be selected over abnormal for safety ECG findings).
- For postbaseline visits:
  - The record closest to the nominal day for that visit will be selected.
  - If there are 2 records that are equidistant from the nominal day, the later record will be selected.
- If there is more than 1 record on the selected day, the worst severity will be taken (eg, abnormal will be selected over normal for safety ECG findings), unless otherwise specified.

### **3.8. Assessment of Coronavirus Disease 2019 Impact**

This study was ongoing during the coronavirus disease 2019 (COVID-19) pandemic.

The assessment of the impact of COVID-19 will be provided in the corresponding sections (eg, Section 4) throughout this SAP. Study drug and study discontinuation due to COVID-19 are described in Section 4.1, study drug interruptions due to COVID-19 are described in Section 4.2, important and non-important protocol deviations due to COVID-19 are described in Section 4.3, and missed and virtual visits due to COVID-19 are described in Section 4.4.

Hematocrit collected from local laboratory and weight measured at home due to COVID-19 impact will be used in CDAI calculations only, and will not be included in the safety laboratory summary (Sections 7.2 and 7.3, respectively). These data will be included in listings, with a flag to indicate which records were collected at a local laboratory or at home, respectively.

## 4. SUBJECT DISPOSITION

### 4.1. Subject Enrollment and Disposition

A summary of subject enrollment will be provided by treatment group for each country, investigator within a country, and overall. The summary will present the number and percentage of subjects enrolled. For each column, the denominator for the percentage calculation will be the total number of subjects analyzed for that column.

A similar enrollment table will be provided by randomization stratum. The denominator for the percentage of subjects in the stratum will be the total number of enrolled subjects. If there are discrepancies in the value used for stratification assignment between the IWRS and the clinical database, the value collected in the clinical database will be used for the summary. A listing of subjects with discrepancies in the value used for stratification assignment between the IWRS and the clinical database at the time of data finalization will be provided.

The randomization schedule used for the study will be provided as an appendix to the CSR.

A summary of subject disposition will be provided by treatment group and overall. This summary will present the number of subjects screened, the number of subjects who met all eligibility criteria but were not randomized with reasons subjects were not randomized, the number of subjects randomized, and the number of subjects in each of the categories listed below:

- All Randomized Analysis Set
- Full Analysis Set
- Safety Analysis Set
- [REDACTED]
- [REDACTED]
- Completed study drug
- Continuing study drug (for analysis other than final analysis)
- Did not complete study drug with reasons for premature discontinuation of study drug
- Completed study
- Continuing study (for analysis other than final analysis)
- Did not complete the study with reasons for premature discontinuation of study

For the status of study drug and study completion and reasons for premature discontinuation, the number and percentage of subjects in each category will be provided. The denominator for the percentage calculation will be the total number of subjects in the Safety Analysis Set corresponding to that column.

The following by-subject listings will be provided by subject identification (ID) number in ascending order to support the above summary tables:

- Reasons for premature study drug or study discontinuation (A separate listing of reasons for premature study drug or study discontinuation due to COVID-19 will be created.)
- Reasons for screen failure (will be provided by screening ID number in ascending order)
- Lot number and kit ID of assigned study medication

## **4.2. Extent of Study Drug Exposure and Adherence**

Extent of exposure to study drug will be examined by assessing the total duration of exposure to study drug and the level of adherence to the study drug specified in the protocol. Summaries of extent of study drug exposure and adherence will be provided by treatment group for the Safety Analysis Set.

A by-subject listing of study drug administration will be provided for subjects with study drug interruption due to COVID-19.

### **4.2.1. Duration of Exposure to Study Drug**

Total duration of exposure to study drug will be defined as last dosing date minus first dosing date plus 1, regardless of any temporary interruptions in study drug administration, and will be expressed in weeks using up to 1 decimal place (eg, 4.5 weeks). If the last study drug dosing date is missing, the latest date among the study drug end date, clinical visit date, laboratory sample collection date, and vital signs assessment date that occurred during the on-treatment period will be used.

The total duration of exposure to study drug will be summarized using descriptive statistics (n, mean, SD, median, Q1, Q3, minimum, and maximum) and using the number (ie, cumulative counts) and percentage of subjects exposed through the following time periods: 1 day, 2 weeks, 4 weeks, 6 weeks, 10 weeks, 14 weeks, 18 weeks, 20 weeks and 24 weeks. Summaries will be provided by treatment group for the Safety Analysis Set.

No formal statistical testing is planned.

## 4.2.2. Adherence to Study Drug

The total number of tablets administered will be summarized using descriptive statistics.

The presumed total number of tablets administered to a subject will be determined by the data collected on the drug accountability eCRF using the following formula. If the bottle was not returned, it is assumed that the subject took all the study drug tablets from the dispensed bottle. The number of tablets returned will be imputed as zero for the given bottle for study drug adherence calculation purpose.

$$\text{Total Number of Tablets Administered} = \left( \sum \text{No. of Tablets Dispensed} \right) - \left( \sum \text{No. of Tablets Returned} \right)$$

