5.2.2. Packaging and Labeling

Filgotinib and PTM filgotinib tablets are packaged in white, high density polyethylene (HDPE) bottles. Each bottle contains 30 tablets, silica gel desiccant and polyester packing material. Each bottle is enclosed with a white, continuous thread, child-resistant polypropylene screw cap fitted with an induction-sealed, aluminum-faced liner.

Study drugs to be distributed to centers in the US, EU and other participating countries shall be labeled to meet applicable requirements of the United States Food and Drug Administration (FDA), EU Guideline to Good Manufacturing Practice - Annex 13 (Investigational Medicinal Products), and/or other local regulations as applicable.

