5.3. Dosage and Administration of Study Drug

The study medication will consist of 200 mg and 100 mg filgotinib tablets for oral administration and PTM 200 mg and 100 mg filgotinib tablets for oral administration.

The following treatments will be evaluated:

- **Treatment group 1:** 1 tablet of 200 mg filgotinib daily, 1 tablet of PTM filgotinib 100 mg daily
- **Treatment group 2:** 1 tablet of 100 mg filgotinib daily, 1 tablet of PTM filgotinib 200 mg daily
- **Treatment group 3:** 1 tablet of PTM filgotinib 200 mg daily, 1 tablet of PTM filgotinib 100 mg daily

Subjects who are non-responders based on the results of the Week 10 assessments (see Section 3.6, Luminal Disease Activity – Non-Response Criteria OR Section 3.7, Perianal Fistulizing Disease Activity – Non-Response Criteria) will be offered the option to receive open-label filgotinib by entering into the LTE study (GS-US-419-3896); prior to entering the LTE study, subjects **must** complete MRI and flexible sigmoidoscopy early termination procedures. Subjects meeting disease worsening criteria after Week 10 must be discontinued from blinded treatment and will be offered the option to receive open-label filgotinib 200 mg (see Section 3.8, Disease Worsening Criteria), except for US males who will be offered filgotinib 100 mg unless they are considered to be ‘dual refractory’ prior to entering the LTE study, subjects **must** complete MRI and flexible sigmoidoscopy early termination procedures. Subjects who complete all procedures per protocol up to the Week 24 visit (including the Week 24 MRI and flexible sigmoidoscopy) will have the option to continue study drug in a blinded fashion in the LTE study.

For missed dose(s) of study medication, subjects should be instructed to take the missed dose(s) of study medication as soon as possible during the same day. If the missed dose is not taken on the original day, then subjects should not take the missed dose and the missed dose should be returned to the study drug bottle. Subjects should be cautioned not to double the next dose (ie, taking the missed dose of study drug with that day’s dose).

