### 4.2.2.1. On-Treatment Adherence

The level of on-treatment adherence to the study drug regimen will be determined by the total amount of study drug administered relative to the total amount of study drug expected to be administered during a subject's actual on-treatment period based on the study drug regimen.

The level of on-treatment adherence will be expressed as a percentage using the following formula:

$$\text{On-Treatment Adherence (\%)} = \left( \frac{\text{Total Amount of Study Drug Administered}}{\text{Study Drug Expected to be Administered on Treatment}} \right) \times 100$$

If the calculated on-treatment adherence is > 100%, it will be set to 100%. Descriptive statistics for the level of on-treatment adherence with the number and percentage of subjects belonging to adherence categories (eg, < 80%, ≥ 80% to < 90%, ≥ 90%) will be provided by treatment group for the Safety Analysis Set.

No formal statistical testing is planned.

A by-subject listing of study drug administration and drug accountability will be provided by subject ID number (in ascending order) and visit (in chronological order).

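### For subjects with unreturned bottles, the adherence rule counts spare and never-due tablets as taken, so reported adherence is biased upward and can reach 100% despite recorded missed doses.

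*SAP*

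**What the plan says.** SAP 4.2.2 computes the tablets administered as the sum of tablets dispensed minus the sum of tablets returned, over the whole study. For a missing bottle, "If the bottle was not returned, it is assumed that the subject took all the study drug tablets from the dispensed bottle", and "The number of tablets returned will be imputed as zero for the given bottle for study drug adherence calculation purpose".

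SAP 4.2.2.1 takes the amount administered "relative to the total amount of study drug expected to be administered during" the subject's actual on-treatment period. The only limit comes at the end: "If the calculated on-treatment adherence is > 100%, it will be set to 100" (per cent). The result is summarised by treatment group, with example categories of below 80%, 80 to below 90%, and 90% or more.

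The end of the on-treatment period can itself be imputed. SAP 4.2.1 says "If the last study drug dosing date is missing, the latest date among the study drug end date, clinical visit date", laboratory sampling date and vital signs date on treatment is used.

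The visible text sets no limit per bottle or per dispensing interval and does not exclude tablets dispensed after the last dose. It plans no count of subjects with unreturned bottles and no sensitivity summary.

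**The concern.** The numerator and the denominator can cover different things. The denominator is one tablet per strength per day up to the last dose. The numerator takes in everything in a missing bottle, whether or not those tablets were ever due. Under Protocol 5.3 a missed dose goes back into the bottle, so returned bottles do record missed doses. An unreturned bottle with spare tablets then offsets those recorded misses, and a cap on the final ratio cannot undo an offset that has already happened inside the sum.

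The error runs in one direction only, because counting a bottle as fully taken can never understate intake. At stake is how the by-arm adherence table, a summary specified in Protocol 8.6.1, can be read. With 15 planned placebo subjects, one subject in the wrong category is 1/15 = 6.7 percentage points. The number of tablets administered, which SAP 4.2.2 also summarises, has no cap at all.

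**Working it through.** The documents state no adherence figure, so there is none to reproduce. The SAP formula is applied directly.

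**Inputs**
- Bottle size: "Each bottle contains 30 tablets" (Protocol 5.2.2).
- Regimen: one tablet of each of two strengths daily, for example "1 tablet of 200 mg filgotinib daily, 1 tablet of PTM filgotinib 100 mg daily" (Protocol 5.3).
- Duration: at most 24 weeks, so 168 tablets per strength (Protocol 3.4).
- Dispensing: Day 1 and Weeks 4, 10, 14 and 18 (Protocol Appendix 2), giving intervals of 28, 42, 28, 28 and 42 days.
- Assumption: each visit supplies the smallest whole number of bottles that covers the interval. More bottles would enlarge the surplus.
- Assumption: true adherence is constant over time, and both strengths behave alike.

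**Surplus.** Bottles per strength are 1, 2, 1, 1 and 2, which is 7 × 30 = 210 tablets against 168 expected. Each 6-week supply has 60 − 42 = 18 spares and each 4-week supply has 30 − 28 = 2. A subject who returns nothing scores 210/168 = 125%, shown as 100% whatever the true intake. The uncapped count for that subject is 420 tablets over both strengths, against 336 in the full regimen.

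**Completer, only the Week 18 supply unreturned.** Reported = min(100%, (a × 126 + 60)/168), where a is true adherence. With the supply limited to its interval, 42 replaces 60. As a lower bound, 0 replaces 60.

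| True | a × 126 | SAP numerator | SAP reports | Interval limit | Lower bound |
|---|---|---|---|---|---|
| 80% | 100.8 | 160.8 | 95.7% | 85.0% | 60.0% |
| 70% | 88.2 | 148.2 | 88.2% | 77.5% | 52.5% |
| 60% | 75.6 | 135.6 | 80.7% | 70.0% | 45.0% |

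The top category starts at 0.9 × 168 = 151.2 tablets, and (151.2 − 60)/126 = 72.4%. A subject truly between 72.4% and 80% therefore moves from the lowest category to the highest through one unreturned supply. A report of 100% needs only (168 − 60)/126 = 85.7% adherence in the returned intervals.

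**Other patterns at 60% true adherence**
- Only the Week 10 supply unreturned: (0.6 × 140 + 30)/168 = 67.9%.
- Week 4 and Week 18 supplies unreturned: (0.6 × 84 + 120)/168 = 101.4%, shown as 100%.
- Week 18 supply unreturned for one strength only, summed over both: (135.6 + 100.8)/336 = 70.4%.
- All bottles returned: 60%, which is correct.

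**Lost just after a dispensing visit, 60% adherence until then.** Earlier bottles are returned and the new supply is not. The last dosing date is missing and is imputed as that visit, so the denominator is the visit's study day.

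| Lost after | Taken before | New supply | Ratio | SAP reports | Interval limit |
|---|---|---|---|---|---|
| Week 4 | 16.8 | 60 | 76.8/29 = 264.8% | 100% | 61.4% |
| Week 10 | 42.0 | 30 | 72.0/71 = 101.4% | 100% | 60.6% |
| Week 14 | 58.8 | 30 | 88.8/99 = 89.7% | 89.7% | 60.4% |
| Week 18 | 75.6 | 60 | 135.6/127 = 106.8% | 100% | 60.3% |

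The interval limit allows one tablet from the new supply here, for the visit day itself, as in (42 + 1)/71 = 60.6%.

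**The case against.** The rule applies only when a bottle is missing, and Protocol 5.7 requires every used and unused bottle to be returned. The documents give no non-return rate. Nothing visible in the inference depends on adherence: the Full Analysis Set needs one dose, no visible endpoint or analysis set uses adherence, and no hypothesis testing is planned. The SAP itself calls the tablet count presumed, and it provides a by-subject listing of drug accountability by visit. All of this stands, and it confines the point to descriptive summaries. It does not correct the by-arm table, which carries no mark for affected subjects. The return requirement also offers nothing once a bottle is missing, which is the only case the rule addresses.

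Three stronger readings are tempting, and the documents do not support them:
- A reader might infer that poor adherers in general appear as about 100% adherent. They do not. Those who return their bottles are scored correctly, and a 60% completer missing one supply is reported at about 68 to 81%.
- A reader might infer that an arm with more early leavers will look better adherent. Withdrawing subjects are to complete early termination and post-treatment assessments (Protocol 3.5.2), and Week 10 non-responders and subjects with disease worsening must have imaging and endoscopy before leaving (Protocol 6.5 and 6.6). They can return bottles at those visits. A subject who stops early is also not expected to be counted to Week 24, because SAP 3.7.1 defines the last dosing date as the date of the last dose taken.
- A reader might infer that under-dosing behind a weak effect could not be recognised. The accountability listing, the exposure summary and the plasma concentration data handled in SAP 3.6 all bear on that, and other pharmacokinetic text may be blacked out.

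**Conclusion.** The point holds for subjects with unreturned bottles. For them the rule can only raise reported adherence. The shift ranges from about 8 percentage points (one 4-week supply missing, 60% true) to about 21 points (the Week 18 supply missing, 60% true). It reaches 30 to 40 points for a 60% adherer lost just after a dispensing visit or missing both 6-week supplies.

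These sizes rest on the assumed minimum bottles per visit, constant adherence and both strengths missing together. The lost-to-follow-up figures also need the last dosing date to be imputed as the dispensing visit. How many subjects would be affected, and whether the arms would differ, cannot be known from the documents. The consequence is a possible overstatement in the adherence and tablets-administered summaries. The efficacy estimates are untouched. Because the error has one direction and the correction is cheap, the rule should be changed.

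**What to change.** In SAP 4.2.2:
1. Limit the tablets counted from an unreturned bottle to those expected in its dispensing interval, up to the last dosing date (or its imputed value under SAP 4.2.1). Where an interval has more than one bottle of a strength, apply the limit to the interval's total. Use the same limited count for the tablets-administered summary.
2. Report by arm the number of subjects with at least one unreturned bottle.
3. Add a sensitivity summary based on returned bottles only, showing subjects with no returned bottle as not evaluable, together with a lower bound that counts unreturned bottles as not taken.

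The first step alone is not enough, because it still assumes full intake within the unreturned interval: a 60% completer missing the Week 18 supply would show 70.0%. The returned-bottles summary recovers the true rate only if adherence was the same in the missing interval, so the lower bound is needed beside it.

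The cost is SAP wording and modest programming on accountability data already collected. Reported adherence will be slightly lower, and some subjects will have no value in the sensitivity summary.
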